8.1 ED Visits and Hospitalizations

The total number of ED visits and hospitalizations reported on the EDV form at the Day 30 follow-up visit, as well as the number reported per participant, will be summarized by evaluation period. Listings of ED visits and hospitalizations, including relationship to substance abuse disorder, will be presented by evaluation period and will include hospitalization or ED Visit date, discharge date, chief complaint, and discharge diagnosis. A listing will also be created for participants enrolled who were later found to have been ineligible, if any follow-up EDV data is available for them.

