10.2.9 Health Services Utilization Inpatient and Health Services Utilization Outpatient²⁹

A brief, structured interview regarding health care utilization (inpatient and outpatient) will be used, which collects information on the type and amount of services received. This includes ED visits, hospitalizations, primary medical care visits (excluding those for buprenorphine treatment and self-help sources of support (e.g., NA)). It is collected at enrollment and at 30 days post study enrollment.

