10.2.18 ED Visits and Hospitalizations

The ED Visits and Hospitalizations form collects information about the index ED visit and any visits or hospitalizations between the index and follow-up. Data is acquired for this form by performing a medical record abstraction.

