14.12 Adverse Events (AEs) and Serious Adverse Events (SAEs)

For the purposes of this protocol, the collection and reporting of safety events will be limited to hospitalization for all medical (including psychiatric) indications, Emergency Department visits, overdoses, and death of any participant enrolled in this study. The study staff will be trained to monitor for and report all protocol-defined safety events including Serious Adverse Events. All safety events, including designated SAEs will be presented to the DSMB. SAEs that are specified for reporting will be reported to the IRB of record per the IRB's guidelines.

Reportable AEs will include:

- None

Reportable SAEs will include:

- Any death for any reason

All deaths, regardless of cause, will be captured for this study. These events will be identified through the participants' locator information or when possible through using state medical examiner records, National Death Index, and review of medical records. Deaths will be reported using the Adverse Event/Serious Adverse Event form set so that appropriate information surrounding the event can be gathered. It is the expectation that all *deaths will be reported in the EDC within 24 hours of site awareness. *Note: only death events that occur within the 30-day follow-up period will be recorded on the AE/SAE form set.

OTHER SAFETY EVENTS OF INTEREST

Hospitalization for all medical (including psychiatric) indications, Emergency Department visits and overdose events will not be captured as AEs or SAEs, but instead will be reported on study specific form(s).

All hospitalization events (including psychiatric indications) as well as Emergency Department visits will be captured for this study using self-report as well as review of medical records. These hospitalizations will be reported on the Health Services Utilization and ED Visits and Hospitalization CRFs. When possible, these forms will confirm the diagnosis for the hospital or ED visit and the information will be verified by study staff. The completion of these forms will indicate whether the information was gathered via self-report or medical record abstraction. This information will be collected at enrollment and at the 30-day follow up visit.

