FSR	Final Study Report
IF	Implementation Facilitation
IFEP	Implementation Facilitation Evaluation Period
ICC	Intra Class Correlation
LN	Lead Node
MAT	Medication-assisted Treatment
NA	Narcotics Anonymous
NIDA	National Institute on Drug Abuse
ORCA	Organizational Readiness to Change Assessment
OUD	Opioid Use Disorder
OTP	Opioid Treatment Program
PARiHS	Promoting Action on Research Implementation in Health Services
PI	Principal Investigator
RA	Research Associate
SAE	Serious Adverse Event
TLFB	Timeline Follow-back
UDS	Urine Drug Screen

LIST OF PATIENT PARTICIPANT eCRFs

Form Code	Form Name
AD1	Adverse Event
AD2	Serious Adverse Event Summary
AD3	Serious Adverse Event Medical Reviewer
CAC	Critical Action Checklist
CCJ	Crime and Criminal Justice
CLG	Contact Log
COM	Communication Log
DEM	Demographics
DM1	Additional Demographics
EC0069B	Enrollment 0069B (Baseline Evaluation)
EC0069C	Enrollment 0069C (IF Evaluation Period)
EC0069P	Enrollment 0069P (Screening)
EDR	ED Visit Review
EDV	ED Visits and Hospitalization
EHQ	ED Health Quiz
EQD	EQ-5D-3L
ESL	ED Daily Screening Log
ETF	Engagement in Treatment: Facility
ETP	Engagement in Treatment: Patient
F69	Timeline Followback Page 2
FLG	Facility Contact Log
FVT	Follow-up Visit Scheduling
HS1	Health Services Utilization Page 1: Inpatient
HS2	Health Services Utilization Page 1: Outpatient
HSI	Health Services Utilization: Inpatient
HSO	Health Services Utilization: Outpatient
HST	Health Status
HVL	Healthcare Visit Logistics
MVF	Missed Visit
NDI	National Death Index

Form Code	Form Name
ODE	Overdose Events
OSU	Other Substance Use
PDR	Protocol Deviation Review
PDV	Protocol Deviation
PES	Patient Eligibility Summary
STC	Study Completion
T69	Timeline Followback Page 1
TAP	TLFB Assessment Period
UDS	Urine Drug Screen

LIST OF PROVIDER PARTICIPANT eCRFs

Form Code	Form Name
D69	Focus Group Demographics
EC0069IB	Enrollment 0069IB (Provider Participant)
FGT	Focus Group Tracking
ICH	Individual Characteristics
OC1	Organizational Readiness to Change Assessment (ORCA) Community
OC2	Organizational Readiness to change Assessment (ORCA+) Community
OE1	Organizational Readiness to Change Assessment (ORCA) ED
OE2	Organizational Readiness to change Assessment (ORCA+) ED
RRL	Readiness Ruler
SC1	Site Characteristics - ED
SC2	Site Characteristics – OTP Page 1
SC3	Site Characteristics – OTP Page 2
SC4	Site Characteristics – OTP Page 3
SC5	Site Characteristics – Community Page 1
SC6	Site Characteristics – Community Page 2
WEL	Introduction

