8.0 SAFETY ANALYSIS

Safety information for patient participants includes self-reported emergency department visits, hospitalizations, overdoses, and suicidal ideation, as well as deaths (not identified from a National Death Index search). Regardless of when the Day 30 follow-up visit occurs, deaths are only collected if the date of death occurred between the index ED visit and Study Day 30 (i.e., the safety window). This information will be summarized separately for those participants who were enrolled and later found to be ineligible. Note that deaths in the safety window are the only reportable adverse events.

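### The safety tables for post-index ED visits and hospitalizations use only the record-abstraction form, although the protocol captures these events by self-report as well and the SAP calls them self-reported

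*SAP*

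**What the plan says.** Protocol 14.12 makes hospitalizations (psychiatric ones included) and ED visits safety events of interest. They are kept off the AE/SAE forms and recorded on study-specific forms. On capture it states: "Emergency Department visits will be captured for this study using self-report as well as review of medical records". It names two forms for reporting, Health Services Utilization and ED Visits and Hospitalization (EDV).

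The protocol describes the two forms differently:

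- Health Services Utilization (protocol 10.2.9) is a structured patient interview at enrollment and at Day 30. On its scope: "This includes ED visits, hospitalizations, primary medical care visits".
- EDV (protocol 10.2.18) covers the index visit and any visits or hospitalizations up to follow-up. On its source: "Data is acquired for this form by performing a medical record abstraction".

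SAP 8.0 opens: "Safety information for patient participants includes self-reported emergency department visits, hospitalizations, overdoses, and suicidal ideation". SAP 8.1 then specifies the summary: "The total number of ED visits and hospitalizations reported on the EDV form at the Day 30 follow-up visit". The listing for participants later found ineligible is made only "if any follow-up EDV data is available for them". SAP 8.1 also says that the listings will show how each event relates to substance use disorder.

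**The concern.** The three statements about the source of these events do not agree. The protocol requires two sources, SAP 8.0 names the patient, and SAP 8.1 uses a form that the protocol says comes from the chart.

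This affects what a reader of the safety section can conclude. Hospitalizations and ED visits never become AEs or SAEs in this trial, so no AE/SAE table stands behind Tables 33-34. If a patient reports an admission at Day 30 that the abstracted records do not show, Table 33 counts that patient as having had none. A reader who relies on SAP 8.0 would also take the tables as patient-reported when, on the protocol's description, they are chart-based.

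**Working it through.** The plan states no figure to reproduce, and the point rests on no sample size, power or event rate. The check compares the texts.

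**1. Which form feeds the tables.** SAP 8.1 names the EDV form for the counts and again for the ineligible-participant listing. The SAP's list of eCRFs identifies EDV as "ED Visits and Hospitalization". Health Services Utilization has its own eCRFs (HS1, HS2, HSI, HSO), and SAP section 8 mentions none of them.

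**2. How EDV is filled.** Protocol 10.2.18 says by record abstraction. Protocol Table 2 agrees: EDV has no minutes against it at follow-up, while Health Services Utilization has 6. The timed Day 30 items account for the whole stated participant time without EDV:

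TLFB 10 + Health Services Utilization 6 + health status 3 + overdose 1 + EuroQol 2 + crime 1 + urine screen 5 + visit logistics 1 + engagement 5 = 34 minutes, which is the total printed in Table 2.

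The schedule therefore gives EDV no patient contact.

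**3. What the shells can hold.** Tables 33 and 34 classify patients as 0, 1, 2, 3, 4, or 5 or more events. They have no row for source and none for unknown. A patient with no EDV event falls in the 0 row whatever the interview recorded.

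**4. Whether the interview data appear elsewhere in the DSC safety output.** The DSC table list (SAP 15.0) shows inpatient and outpatient counts only at baseline (Tables 11-12). Day 30 utilization is secondary effectiveness outcome 4 (SAP 7.6.2; protocol 8.4), and SAP Table 1 assigns that analysis to the Lead Node. Tables 33-34 are therefore the only listed DSC safety tables for post-index ED visits and hospitalizations, and they hold the abstracted events.

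**5. The promised listing field.** Listings 1-4 carry site, participant ID, index date, event date, discharge date, chief complaint and discharge diagnosis. No column shows the relationship to substance use disorder.

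**6. Size.** The documents give no ED-visit or hospitalization counts by source. They also do not say whether EDV abstraction reaches beyond the site's own records. The number of omitted events cannot be derived.

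**The case against.** The strongest reply is that the omission of events is inferred and not demonstrated. Protocol 14.12 adds that completing the two forms will show whether information came from self-report or abstraction. That can mean that the choice of form identifies the source, or that each form carries a flag. On the second reading EDV could hold self-reported events, and SAP 8.0 and 8.1 would fit together. The eCRF itself is not in the documents. This stands as a limit on the size of the problem. It does not remove the conflict, because protocol 10.2.18 would then still describe EDV wrongly.

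A second reply is that 14.12 is a rule for capture and does not prescribe tabulation. An abstracted count does not depend on the patient attending Day 30, so EDV is a reasonable main source. That is right, and it is why the EDV counts should stay.

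A third reply is practical. Protocol 10.2.9 describes the interview as recording the type and amount of services. Nothing shows that it holds the dates and diagnoses needed to match events or fill Listings 1-4. This also stands, and it limits what can be asked for.

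A reader might infer more than the documents support:

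- **That these are the only safety displays of serious non-fatal events.** They are not. Table 35 and Listing 5 cover overdose, including days needing medical assistance, and Table 36 and Listing 7 cover suicidal ideation.
- **That the safety tables will contradict the utilization outcome within one report.** The Lead Node handles that outcome, so a common report is not established. Two measures from different sources may also differ without error.
- **That a stated share of events is missed, or that the share differs by evaluation period.** The documents supply no basis for either.
- **That the self-reported events are lost.** They are collected and feed a secondary outcome.

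**Conclusion.** The point holds as a conflict over data source and as a gap in descriptive safety reporting. SAP 8.0, SAP 8.1 and protocol 14.12 cannot all be followed as written. On the protocol's description of the forms, ED visits and hospitalizations known only from the Day 30 interview are left out of Tables 33-34 and Listings 1-4.

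The conclusion rests on two assumptions: that EDV is filled only by abstraction, as protocol 10.2.18 says, and that some post-index care is absent from the records abstracted. If EDV also accepts self-report, the omission shrinks and what remains is mainly wording. The number omitted cannot be estimated from the documents. The tables are descriptive, so no primary or secondary inference changes. The missing listing column is a separate, smaller defect that does not depend on either assumption.

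**What to change.** - **Tables 33-34:** keep the EDV counts. Beside them show, by evaluation period, the number of patients with at least one hospitalization (Table 33) or ED visit (Table 34) by self-report on the Day 30 Health Services Utilization forms, and the number by either source. Give the Day 30 attendance denominator for each period next to the self-report figures.
- **Source split:** report EDV only, self-report only and both, or de-duplicate events, only if the collected fields allow it.
- **SAP 8.0:** replace the self-reported label for these events with the actual source of each count. If the EDV eCRF does accept self-report, say so and reconcile that with protocol 10.2.18.
- **Listings 1-4:** add the column for relationship to substance use disorder that 8.1 promises.

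The cost is SAP wording and some extra programming on data already collected. The limitation is that self-report is missing for patients who did not complete follow-up. The either-source count is therefore less complete for them, and the denominators must be shown.

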8.2 Overdose Events

Overdose events reported on the ODE form at the Day 30 follow-up visit will be summarized by evaluation period. A listing of overdose events report at the follow-up visit will be presented by site for each evaluation period and will include number of days the participant overdosed on opioids and the number of days the participant needed medical assistance for an opioid overdose in the past 30 days. A listing will also be created for participants enrolled who were later found to have been ineligible if any ODE data is available for them at the follow-up visit.

8.3 Suicide Risk

A listing of patient participants endorsing suicidal ideation on the HST at baseline or the Day 30 Follow-up visits will be presented for each evaluation period by site. A listing will also be created for participants enrolled who were later found to have been ineligible. Patient participants are considered to have endorsed suicidality on the HST if they indicate several days, more than half the days, or nearly every day having thoughts they are better off dead or of hurting themselves.

8.4 Deaths

Deaths occurring in the safety window will be coded using the MedDRA® dictionary version 23.1. A listing of deaths will be presented by evaluation period and will include description of death, date of enrollment, date of death, relatedness to overdose, MedDRA® coded Preferred Term and

System Organ Class. A listing will also be created for participants enrolled who were later found to have been ineligible. Narratives of deaths will also be provided.

9.0 SIGNIFICANCE TESTING AND MULTIPLICITY

As this study is designed as a Hybrid Type 3 Effectiveness-Implementation study, the implementation is the main outcome, and so when measuring success of the study, the implementation outcome will take precedence over the effectiveness outcome, which will be considered secondary. Therefore, considering the effectiveness aim as secondary, it is not necessary to put in procedures to control the type 1 error across multiple outcomes. Multiple-comparison adjustments are not anticipated when performing secondary analyses. To be mindful of the multiple testing problem, secondary findings will be reported as noteworthy hypothesis-generating results only when their p-values are considerably smaller than 0.05.

10.0 SAMPLE SIZE AND POWER

This section presents power simulation for the implementation of the primary outcome. The power simulations to assess the adequacy of the sample size followed the method of Parzen⁶. The Parzen method simulates many vectors of $(0,1)$ random variates with specified probabilities and a specified positive intraclass correlation (ICC) ρ , for a given sample size. Assuming 240 patients will be enrolled at each of the 4 sites, power simulations were done for four parameter sets (scenarios) under both the alternative and null hypotheses as a function of an assumed ICC. The first 120 elements of each vector all had a common probability p_1 , while the second 120 elements had a common probability p_2 , where (p_1, p_2) are assumed probabilities of success in the baseline and IF evaluation periods, respectively. Each vector thus specifies in its first half a site's outcomes in the baseline evaluation period, while in the second half it specifies outcomes in the IF evaluation period. Four such vectors (one for each site) comprised the data for a single iteration of the simulation. Each element in each vector was assigned a month as per the protocol study timeline. However, month by itself played no role in determining the probability of success of any vector elements. For each setting of the parameters (p_1, p_2, ρ) , 10,000 replicates were generated (that is, 40,000 vectors) for simulation analysis.

A Stepped-Wedge model was used to analyze simulated data. Simulated power was taken to be the proportion of the 10,000 GLIMMIX runs that had a significant one-tailed type 3 p-value for arm at alpha level 0.05. The “arm” refers to baseline (control) and IF evaluation (intervention) periods. Power analysis were not adjusted/ controlled for type I error. Because in this study it is likely the implementation outcome will have a low probability in the baseline evaluation period coupled with a large ICC, other analytical methods were identified that had better power characteristics than the GLIMMIX approach outlined above. One method is to substitute historical data for the relevant site(s) for the data in the “all zeros” arm. Problems with this approach are (1) there is no guarantee that the historical data will not be “all zeros”, and (2) it is difficult to simulate the effect of this policy beforehand. The following section presents power analysis for another alternative approach, ChangeToOne policy, and a final approach, Bayesian analysis, is outlined in Appendix 15.0.

Details of the power simulations and results are given in Section 12 of the protocol.

10.1 ChangeToOne Policy

This rather naïve approach actually results in a surprisingly beneficial effect on the “Implementation Outcome with low p_1 ”, without appreciably changing power for the other scenarios (in which the probability of an “all zero” site-arm is very low, so the ChangeToOne policy seldom has an effect).

10.1.1 Bayesian Approach

A Bayesian approach, which has its own attractions and drawbacks, was also considered. We detail these in the Appendix of the SAP (Section 17.0). Based on the power calculations previously presented, having sites with “all zeros” in the BEP degrades power no corrective action is made. While the “ChangeToOne” policy seems a simple and attractive remedy, the Bayesian approach with diffuse priors leads to similar conclusions. Except for the credibility intervals for $p_2 - p_1$, increasing ICC degrades precision. Due to these findings and the interpretational focus on the risk difference, the main analysis of the primary implementation will utilize the Bayesian approach, with diffuse priors, instead of the ChangeToOne Approach, as noted previously in Section 7.2.1.

10.2 Summary of Power Simulations

Under the most optimistic scenarios investigated (Implementation Outcome with low p_1 and Efficacy Outcome with high p_2) and $ICC < 0.3$ (and perhaps higher), power for the envisioned design exceeds 0.8 under the ChangeToOne policy and Bayesian approach. Other scenarios featuring less separation between groups have lower power. Having sites with “all zeros” in the baseline arm degrades power if you take no corrective action. The “ChangeToOne” policy seems a simple and attractive remedy. A Bayesian approach with diffuse priors leads to conclusions similar to those from the ChangeToOne policy (see Appendix 17.0). Except for the credibility intervals for $p_2 - p_1$, increasing ICC degrades precision.

11.0 INTERIM ANALYSES AND DATA MONITORING

No interim looks at primary or secondary outcomes were planned for this study. However, a power and sample size recalculation was to be performed based on the primary outcome rates and enrollment rates observed in the baseline evaluation period. The power and sample size recalculation was to be done no earlier than the end of the first site’s baseline evaluation period.

Due to extremely low recruitment at one site, and fairly low recruitment at another site during the BEP, alternate power and sample size recalculations were implemented to evaluate the impact of this and several possible design changes. The first evaluation, in December 2017, simulations were conducted for the following scenarios:

- assumed future enrollment rates would proceed as expected for all sites;
- observed enrollment rates would continue for the remainder of recruitment at all sites;
- add three months of recruitment to each evaluation period and assume expected recruitment rate at all sites going forward;
- add three months of recruitment to each evaluation period and assume observed recruitment rates at all sites going forward;
- extend the IFEP by six months assuming expected enrollment rate for all future enrollments; and
- extend the IFEP by six months assuming all future recruitments occur at the observed rate.

These power curves did not indicate any substantial improvement over the original calculations in the protocol, and no changes were made to the design.

The second evaluation occurred in June 2018 when it was observed that the other two sites would exceed the target sample size of 120 in the BEP. The question of interest was whether recruitment should be slowed down at these high enrolling sites. Three different patterns of recruitment were

considered for the IFEP, with none showing substantial changes in power. No changes were made to the study implementation or expected recruitment rates for each site.

12.0 DATA QUALITY

12.1 Data Audits

A summary of data audit results from site interim monitoring visits conducted by CCC monitors will be presented by site.

